11.3 Statistical methods

11.3.1 Definition of the analysis populations

Intention-to-Treat (ITT)

The intention-to-treat (ITT) population will include all patients enrolled in the study and randomised with at least one observation made after randomisation.

The primary efficacy analysis will be performed in the ITT population.

All variables collected will be analysed in the ITT population.

Per-Protocol (PP)

The Per-Protocol population will include all ITT patients who do not have major study plan deviations. A protocol deviation will be classified as "major" if it significantly affects the main target parameter (90-day mortality).

In particular, administration of albumin in the interest of patient safety outside the limits specified in the interventional group, albeit approved by the protocol, will always result in exclusion from the PP analysis.

As a sensitivity analysis, the primary efficacy analysis will be repeated in the PP population. If there are differences between the randomised and the actual treatment, an additional sensitivity "as-treated" analysis will be performed.

Details on trial protocol deviations will be described in the statistical analysis plan.

Listing-Only-Set (LOS)

Data from all patients not included in the ITT analysis can be listed as needed. The reasons for the exclusion will be recorded and analysed as far as possible.

Safety Analysis

The safety analysis will be carried out in the ITT group.

11.3.2 Data analysis

General methodology:

All collected data will be analysed using descriptive methods in the two treatment groups. This includes at least:

- the number of values collected and missing, mean, standard deviation, minimum, quartiles including median and maximum for continuous variables and
- frequency analyses for ordinal and categorical data.
- At baseline, the last available value will be used no later than the period up to 2 hours after randomisation, but before the start of albumin administration.

Baseline and population characteristics, demographics:

Demographic variables, SAPS II, APACHE II: descriptive analysis

Primary analysis:

The primary endpoint, "90-day mortality" (M90), will be calculated using a generalised mixed model with the random effects "centre" and "patient in centre" and the fixed effects SAPS II, SOFA and "baseline serum albumin value" as well as " treatment group "to the significance level Alpha = 0.05 analysed bilaterally.

The null hypothesis, M90 (control group) = M90 (albumin infusion), will be tested against the alternative M90 (control group) \neq M90 (albumin infusion).

The primary analysis will be conducted in the ITT population.

Additional sensitivity analyses:

- Analysis in the PP population
- If more than 10% of M90 data are missing: multiple imputation analysis based on observed mortality rates, SOFA scores, ICU stay, and hospital stay.

Secondary endpoints:

- 28-day, 60-day, intensive care and hospital mortality: descriptive statistics, Kaplan-Meier estimates on mortality.
- Organ failure defined as increase in the daily recorded SOFA (day 1 to 28) from a value <2 to a value ≥ 2, individual number of organ failures in the period from day 1 to day 28: descriptive statistics, Kaplan-Meier estimates for the date of the individual first organ failure
- SOFA score: descriptive statistics
- Length of stay (after randomisation, until first discharge) in ICU, hospitalisation after randomisation (until first discharge to rehabilitation, transitional care, long-term care or home): descriptive statistics, Kaplan-Meier estimates, censored after drop-out and death.
- Ventilation-free days, vasopressor-free days until (first) discharge of ICU or maximum 28 days: descriptive statistics
- Total amount of fluid administration in the ICU (individual average amount of fluids given enterally or parentrally, including volume therapy) and total fluid balance in the ICU (individual average difference between daily fluid administration urinary output and other fluid loss): descriptive statistics, especially quartiles.

All secondary endpoints, unless included in the primary analysis model, will be exploratively compared using appropriate parametric and nonparametric tests between treatment groups.

Health economics:

In the context of the ARISS study, a health economic cost-benefit analysis of volume replacement therapy of the ICU stay will be carried out up to a maximum of day 28. The direct costs of colloid, crystalloid and albumin administration will be recorded and the length of stay (first hospitalisation and stay since study participation) evaluated economically to assess whether albumin administration has an effect on hospital costs or not. At the patient level, DEALE (declining exponential approximation of life expectancy) (27) will be applied to calculate patient-specific life expectancy based on mortality rates in the general population and in the disease-specific population. The subsequent cost-effectiveness analysis will yield the cost per year of life for albumin administration. The robustness of the analysis will be checked with one-way and multi-way analyses as well as probabilistic sensitivity analysis.

Analysis of safety parameters:

Frequencies of AEs and SAEs will be analysed using frequency tables. In addition, frequencies of selected AEs (sepsis-related clinical events) will be analysed.

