1.5 Overview (flowchart) of the clinical trial process

1.6 Schedule of the trial visits

		eening/ seline	maximal treatment duration with human albumin 20% (200 g/l, Infusionslösung) in the ICU			Data collection at discharge from the hospital or at the end of the tria	Data collection (if necessary by phone)
Procedure, Event	24 h period before Randomisation	Randomisation (max. 2h after informed consent)	until 2 h after Randomisation and 6-24h after the onset of septic shock	6 h after Randomisation	Study day 1 until max. 28 days after randomisation		Day 28, 60 and 90
Checking inclusion and exclusion criteria	Х						
Written informed consent	Х						
Pregnancy test (female patients in childbearing age) ¹	Х						
Collection of basic data ²	Х						
Documentation of primary and secondary admission diagnoses	Х						
Documentation of comorbid conditions	Х						
Documentation of data on infection, microbiology and anti-	1						
infective therapy (continuous collection of data)	\leftarrow						
Collection of data on SAPS II-/APACHE II-Scores	Х						
Collection of data for calculation of SOFA-Scores	Х				X		
Determination of serum albumin levels			X 3		X		
Administration of the trial drug in the albumin group			Х		X, Dose adjustment according to serum albumin levels		
Documentation of albumin adminstration (continuous)			~		———	•	
Detection of clinical parameters ⁴	Х	Х		Х	X		
Documentation of concomitant medications	X 5	X 5		X _e	X		
Collection of the results of routine laboratory parameters ⁷		X ₈		Х	X		
Documentation of procedures in the ICU 9	Х	Х		Х	X		_
Collection of AEs, SAE, sepsis-related clinical events 10		\leftarrow				· (X)	(X)
Collection of data on the vital status 11				Х	X	Х	Х
Collection of data on ICU length of stay						Х	
Collection of data on hospital length of stay						Х	

¹ After obtaining informed consent

³ Albumin group: Determination of serum albumin concentration before administration of the starting dose of the trial drug

⁴ Body temperature, respiratory rate and haemodynamic parameters (SAP, MAP, DAP, CVP, CO)

⁵ Catecholamines, inotropic agents, diuretics, volume replacement therapy, including blood transfusion, adjunctive sepsis therapy

⁶ Recording of concomitant medication with catecholamines and inotropes at the corresponding time point (+/- 1 hour); recording of concomitant medication with diuretics, volume therapeutics including transfusion therapy, adjunctive sepsis therapy) of the previous 6 h

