7.3 Time period until 2 h after randomisation

- Collection of data on infection, microbiology and anti-infective therapy
- Capture of AEs, SAEs, sepsis-related clinical events
- Procedure according to group allocation:

Albumin group:

- 1. Blood sampling to determine serum albumin concentration within 2 hours after randomisation
- 2. Starting dose of the trial product within 6-24 h after the onset of septic shock: 60 g Human albumin 20% (200 g/l solution for infusions) over 2-3 h
- 3. Data collection trial drug on administration (continuous collection).

Control group without albumin:

- 1. Blood sampling to determine serum albumin concentration within 2 hours after randomisation
- 2. Treatment according to usual practice with crystalloids as the first-choice fluid treatment.

Study protocol, Version 3.0

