11.2 Randomisation

Randomisation will be stratified according to:

- Serum lactate levels within 24 h before inclusion in the trial: ≤ 8 mmol/l vs. > 8 mmol/l and
- centre

in the treatment groups

- albumin group
- control group without albumin

Albumin administration will be adjusted after the starting dose according to serum albumin concentrations. Therefore, blinding will not be possible.

Group assignment will be determined using a validated electronic tool (PaRANDies) after inclusion of the patient. Randomisation will be based on a randomisation list created in advance with nQuery Advisor 7.0.

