6.6 Primary Analysis

The primary efficacy variable 90 day mortality will be analyzed with a Generalized mixed model with fixed effects SAPS II score, baseline lactate, baseline-albumin-serum value, type of admission (surgical/non-surgical) and treatment group and random effect center; descriptive statistics will be presented. The primary analysis will take place in FAS according to ITT-principle; an additional sensitivity analysis in PPS will be performed. In addition, descriptive analysis of 90-day mortality in subgroups with respect to baseline-lactate, baseline albumin, baseline SOFA, SAPS II und APACHE II will be performed.

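### Baseline serum albumin, a covariate in the primary model, is scheduled after open-label allocation, with a window that can close earlier in one arm and no rule for missing values

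*Protocol*

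**What the plan says.** **Role of the covariate.** SAP 6.6 specifies a generalised mixed model with "fixed effects SAPS II score, baseline lactate, baseline-albumin-serum value, type of admission (surgical/non-surgical) and treatment group and random effect center". Protocol 11.3.2 has a different covariate list, but baseline albumin is in it too. SAP 6.9 also forms four subgroups by baseline albumin.

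**Definition of baseline.** Protocol 11.3.2 uses the last available value "no later than the period up to 2 hours after randomisation, but before the start of albumin administration". SAP 5.3 states a baseline time frame for SOFA and for physiological data, but none for albumin.

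**When the sample is taken.** Protocol 7.3 lists the same line under the albumin group and under the control group: "Blood sampling to determine serum albumin concentration within 2 hours after randomisation". Protocol 6.3.1 requires a sample before the starting dose, which only the albumin group receives, and allows at most 2 h from randomisation to the start of that dose. Footnote 3 of the visit schedule (1.6), attached to this determination, reads "Albumin group: Determination of serum albumin concentration before administration of the starting dose of the trial drug". The synopsis mentions a draw up to 2 h after randomisation where necessary, and names no arm.

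**Blinding.** Protocol 11.2: "Therefore, blinding will not be possible".

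**Missing values.** SAP 5.1 carries forward short gaps in the Glasgow Coma Scale and replaces nothing else. The multiple imputation in Protocol 11.3.2 is triggered only by missing 90-day mortality.

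**The concern.** Adjusting for a covariate leaves a randomised comparison intact when the covariate is fixed before allocation, or at least cannot be affected by it. Staff know the allocation when this sample is drawn. Three things can then differ by arm.

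- **Timing.** The start of albumin ends the window in one arm only. A later sample follows more fluid, so measured albumin could be lower for reasons unrelated to prognosis.
- **Completeness.** In the albumin arm the starting dose prompts the draw. In controls only 7.3 does, and footnote 3 can be read as not asking for it.
- **Who is analysed.** With no replacement rule, a mixed model omits any patient whose covariate is missing. The primary analysis would then cover fewer patients than the full analysis set that SAP 6.6 names, possibly unequally by arm.

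At stake are a small distortion of the adjusted treatment effect, some power, and the claim that the primary analysis follows intention to treat.

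**Working it through.** **1. The plan's own figure.** Inputs from the sample size section of Protocol chapter 11: 50% against 42.5%, two-sided 0.05, power 80%, 706 per arm, 15% dropout. The pooled two-proportion formula gives 693 per arm (1386), and 719 per arm (1438) with continuity correction. The planned 1412 lies between them. At 706 per arm the power is 80.7%. Dropout: 1412 / 0.85 = 1661.2, rounded up to 1662. The figure reproduces. The synopsis rate of 42% is a separate matter and is not used here.

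**2. Where each model covariate comes from.**

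| Covariate | Scheduled source |
|---|---|
| SAPS II, SOFA | 24 h before randomisation (7.1) |
| Type of admission | basic data, before randomisation (7.1) |
| Lactate | routine laboratory, 24 h before randomisation (7.2) |
| Serum albumin | within 2 h after randomisation (7.3) |

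Albumin is not in the routine laboratory list for the pre-randomisation period, and the schedule marks no albumin determination in the screening or randomisation columns.

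**3. The window by arm.** In the albumin arm it closes at the start of the infusion, anywhere from 0 to 2 h after randomisation. In controls it normally closes at 2 h. The possible difference is therefore at most 2 h.

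**4. Effect of a timing difference.** Target log odds ratio: ln[(0.50/0.50) / (0.425/0.575)] = 0.302, an odds ratio for death of 0.739 for albumin.

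If control values read lower by d g/l only because they are drawn later, and the log-odds of death rise by b per g/l of lower albumin, the adjusted treatment effect moves by about b × d. Controls look sicker than they were, so the move is against albumin. Both inputs are assumed.

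- d = 0.2, b = 0.03: 0.006, and 0.006 / 0.302 = 2%
- d = 0.5, b = 0.05: 0.025, and 0.025 / 0.302 = 8%

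In power terms, the standard error of the log odds ratio is √[1/(706 × 0.25) + 1/(706 × 0.425 × 0.575)] = 0.107.

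- No shift: 0.302 / 0.107 − 1.96 = 0.86, power 80.6%
- Shift 0.006: 0.296 / 0.107 − 1.96 = 0.81, power 79%
- Shift 0.025: 0.277 / 0.107 − 1.96 = 0.63, power 73.6%

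A wider assumed range (d from 0.5 to 2 g/l, odds ratio for death 0.97 to 0.93 per g/l) gives shifts of 0.015 to 0.145. The planned 0.739 would read 0.750 to 0.855, and a true odds ratio of 1 would read 1.015 to 1.156. The upper end needs a systematic 2 g/l gap arising within 2 h. If sampling times do not differ by arm, the shift is zero.

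**5. Effect of missing control samples** (share assumed, 706 kept in the albumin arm):

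| Controls missing | Controls analysed | Power |
|---|---|---|
| 0% | 706 | 80.7% |
| 5% | 671 | 79.7% |
| 10% | 635 | 78.6% |
| 20% | 565 | 76.0% |
| 30% | 494 | 72.8% |

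Five per cent is 35 of 706 evaluable controls, or 42 of 831 randomised. The table covers power only. If the missing controls differ in prognosis, the estimate moves as well, in a direction the documents do not determine.

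**The case against.** The plan can be defended on several points, and most of them limit the finding.

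- **A reader might infer that the sample is taken only in the albumin group.** The documents do not support that. Section 7.3 expressly requires it in controls, the schedule row has no arm restriction, and footnote 3 can be read as setting the timing where there is a starting dose. What stands is an ambiguity between the footnote and 7.3.
- **A reader might infer that trial drug contaminates the baseline value.** The rule prevents this by requiring a value from before albumin starts. That condition is a safeguard. Its side effect is to shorten the window in one arm.
- **A reader might infer that only control samples follow post-allocation crystalloid.** Both groups receive crystalloids under usual practice (the general remarks of chapter 7), and both share the 2 h cap. Nothing shows that controls get more fluid or are sampled later in that window.
- **Not every value need be post-allocation.** A pre-randomisation result can qualify as the last available one. Nothing requires it to be collected, however, so the post-allocation draw remains the scheduled case.
- **A reader might infer that bias is established, or that it could create a false benefit.** Neither follows. The size rests on assumed inputs, and the timing mechanism works against albumin.
- **Exclusion of patients with a missing covariate** is an inference from SAP 5.1 and ordinary model fitting. The SAP does not state it. No missingness rate is given.

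**Conclusion.** The point holds as a minor, inexpensive correction. A primary-model covariate is scheduled after open allocation, its window can close earlier in one arm, footnote 3 and section 7.3 need reconciling, and the SAP gives neither a time window nor a missing-value rule for it. Bias is possible but not demonstrated, and it disappears if sampling time and completeness are equal between arms.

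The distortion is probably small: 2-8% of the target log odds ratio, against albumin, if controls read 0.2-0.5 g/l lower and the log-odds change by 0.03-0.05 per g/l. Neither input is in the documents, and larger assumed inputs give larger shifts. Even the upper end of the smaller range would cost about 7 points of power. Losing 5% of controls costs about 1 point. The planned 1412 and 1662 are unaffected.

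**What to change.** 1. **Sampling (Protocol 7.2, 7.3 and schedule).** Draw the albumin sample in every patient after consent, or the substitute procedure used locally, and before the allocation is retrieved. Section 7.2 allows up to 2 h between consent and randomisation.
2. **Definition (Protocol 11.3.2 and SAP).** Baseline albumin is the last value at or before randomisation. Only if none exists, use the first value within 2 h after randomisation and before any albumin, in either arm. The pre-albumin condition must stay in the fallback, otherwise a post-infusion value could count as baseline.
3. **Consistency.** Align footnote 3 with 7.3, so that both state the sample for both arms.
4. **Missing values (SAP 5.1 and 6.6).** Keep patients without the value in the primary model by a rule that ignores arm, such as simple imputation from the pooled baseline data.
5. **Reporting.** Give missingness and sampling time of baseline albumin by arm, and add a sensitivity model that omits the covariate.

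The cost is protocol and SAP wording and the same blood draw taken slightly earlier. A few samples will come from patients who are consented but not randomised. If recruitment has begun, items 2, 4 and 5 can still be set in the SAP before outcomes are analysed by arm. Patients already enrolled without a pre-randomisation value would fall under the fallback, so the sensitivity model matters more for them.

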1.1 Overview of the clinical trial

	Randomised controlled multicentre study of albumin	
Title of the trial	replacement therapy in septic shock	
Trial Acronym	ARISS-Study	
Sponsor according to AMG	Friedrich Schiller University Jena	
Sponsor's legal representative (SpB) and principal investigator (LKP)	[name]. [name] Universitätsklinikum Jena Klinik für Anästhesiologie und Intensivmedizin [name] [contact] [contact] E-Mail: [contact]	
EudraCT Number	2018-001874-89	
Study population	Female and male patients ≥ 18 years treated in the intensive care unit (ICU) within 24 hours of septic shock diagnosis	
Study phase	III b	
Trial design	Prospective, multicentre, randomised, controlled, parallel- grouped, open-label, interventional clinical trial according to the German Medicinal Products Act	
Primary target: To investigate whether albumin administration and maintenance of serum albumin concentrations of a 30 g/l in the ICU for up to 28 days after the onset of shock, will reduce total 90-day mortality compared volume replacement therapy without albumin Secondary targets: - To investigate whether albumin administration at maintenance of serum albumin concentrations of 30 g/l in the ICU for up to 28 days after the onset septic shock would influence ICU, hospital, 28-a day mortality rates, rates of organ dysfunction/far assessed by the SOFA score, ICU/hospital length stay, ventilator and vasopressor-free days. - Cost-benefit analysis of volume replacement the		
Primary outcome (primary	from ICU admission until maximum day 28 Primary outcome: 90-day all-cause mortality	
end-point)		
Secondary outcome	Secondary outcomes:	
(secondary end-point)	 - 28- and 60-day mortality, mortality rates in the ICU and during hospitalization, organ dysfunction/failure as assessed by the SOFA score, ICU and hospital length of stay, ventilator and vasopressor free days. 	

ARISS
EudraCT-Nr.: 2018-001874-89
ZKSJ0112_ARISS
UNIVERSITATS
KLINIKUM
Jena

Sample size	 Cost-benefit parameters of volume replacement therapy (albumin, other colloids and crystalloids) Total amount of fluid of fluid administration and total fluid balance in the ICU. Safety related endpoints: Onset of AEs and SAEs, in particular anaphylactic shock, hypervolaemia, pulmonary oedema and sepsis-related clinical events Assuming a 90-day mortality of 50% in the control group without albumin and 42% in the albumin group, 1412 patients need to be evaluated (power: 80%, Chi²Test alpha

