7.5.2 Data collection at trial days 28, 60, and 90 after randomisation

At these time points, data will be collected on the primary and secondary "mortality" outcomes. If the patient has already left the hospital before these time points, contact with the patient, his quardian or legal representative will take place to collect the required data.

- Vital status (alive/dead): if applicable date of death and cause of death; if applicable, recording of "end of life" decisions, stay after discharge
- · Verification of the documentation of SAEs already detected and serious sepsis-related clinical events, possibly AEs, which are "ongoing" at the respective time point

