10.3 Audits and inspections

Within the scope of quality assurance, the SpB can have an independent audit conducted at any time in the participating institutions. In this case, the investigator or the participating institution will grant the auditor access to all documents necessary for the audit.

Inspections as part of the monitoring of ongoing or already completed clinical trials are carried out by the competent authority in accordance with § 64 (1) of the AMG (28). The inspection conducted by the competent authority shall be carried out in accordance with a written procedure and a pre-determined plan.

The SpB and all participating trial centres are committed to supporting inspections by competent authorities and, in this regard, to grant authorised persons access to the original data and documents.

Statistical methods and determination of sample 11. size

Sample size

The 90-day mortality in the control arm is estimated to be about 50% (taking into account the possible use of albumin in the control group) (4, 7, own pilot study).

For the sample size estimation, a 15% reduction in 90-day mortality is assumed, i.e., an absolute reduction of 7.5 percentage points to 42.5% (relative risk 1.18). This limit was chosen because the relatively costly albumin therapy can only be justified if there is a sufficiently clear treatment effect. This assumed effect size has the potential to affect current standard of care and international treatment guidelines and lies between the observed reduction in 90-day mortality in patients with septic shock (13%) and the assumed effect size in the ALBIOS study (23). Following the recommendation of the reviewers of the DFG application of the ARISS study, the sample size was estimated taking into account a centre variability (probably about 50 centres) in mortality of patients in the control arm of the study between 40% and 60% and a risk reduction between 12% and 18% (coincidentally uniform).

A Mantel-Haenszel Chi² test at a two-tailed significance level of 0.05 with a power of 80% requires 1412 patients to be analysed, 706 per arm, to demonstrate such an effect.

This case number estimate can be considered conservative for the planned analysis (nonlinear mixed model taking into account random centre effects).

The case number estimation was performed using SAS 9.4 (SAS Institute Inc., Cary, NC, USA).

Dropout Rate:

Approximately 15%, through

- "loss to follow up" until day 90

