- refusal to continue in the clinical trial by incapacitated patients who regain their capacity to consent. and
- failure to consent to the continuation of the clinical trial by the guardian or the legal representative within the respective time windows in patients who became participants after confirmation of the urgency of participation in the clinical trial by an independent consultant or other procedures, established in the trial centres to include patients who are aunable to provide informed consent (VISEP 10.5%). MaxSep 8.2%) (25, 26).

Assuming a dropout rate of 15%, 1662 patients need to be randomised.

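### The protocol's predictor list for imputing missing 90-day mortality names neither treatment arm nor last known vital status, and the SAP drops the imputation without saying so

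*Protocol*

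**What the plan says.** Protocol 11.3.2, under additional sensitivity analyses, states: "If more than 10% of M90 data are missing: multiple imputation analysis based on observed mortality rates, SOFA scores, ICU stay, and hospital stay". This is the only description of an imputation for the primary endpoint in either document. It does not say whether the mortality rates are overall or by arm, or at which time points. It also does not say whether SOFA is the baseline or the daily score.

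The protocol's primary model (11.3.2) has SAPS II, SOFA, baseline serum albumin and treatment group as fixed effects, with centre random. The SAP's version (6.6) has SAPS II, baseline lactate, baseline albumin, type of admission and treatment group, again with centre random. Of all these terms, only SOFA is on the imputation list.

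On the amount of missing data, Protocol 11.1 says: "Assuming a dropout rate of 15%, 1662 patients need to be randomised". The causes given are loss to follow-up, refusal by patients who regain capacity, and failure to obtain a representative's consent in time. No split between them is given.

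Protocol 7.5.2 collects at days 28, 60 and 90: "Vital status (alive/dead): if applicable date of death and cause of death". Section 7.5.1 collects the same at hospital discharge.

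SAP 5.1 allows replacement only for short gaps in the Glasgow Coma Scale. All other missing values stay missing, and missing 90-day mortality is taken into account only in the Kaplan-Meier analysis. SAP 6.6 names only the per-protocol sensitivity analysis. SAP 6.11, the list of deviations from the protocol, mentions only the subgroup cut-points.

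**The concern.** Two pieces of information that an imputation of a binary mortality endpoint needs are not named.

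The first is treatment arm. If missing outcomes are drawn from a model that does not know the arm, patients with the same predictors receive the same death probability in both arms. The imputed part of the data then carries no direct treatment effect, and the estimated difference shrinks.

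The second is survival to last contact. A recorded death settles the endpoint, so any patient whose 90-day status is missing was alive when last seen. A model fitted to all patients, about half of whom are expected to die, many perhaps in hospital, can give such a patient too high a risk. Length of stay alone does not settle this, since a stay of a given length can end in death or in live discharge.

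At stake is the credibility of the analysis meant to show that the primary result survives missing data. Imputed without arm, a real effect would look more fragile than it is. As the SAP stands, the analysis would not be run at all.

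**Working it through.** **Inputs from the documents.** Control mortality 50%, albumin 42.5%, difference 7.5 points (Protocol 11.1); two-sided alpha 0.05, power 80%, 706 per arm (11.1); 15% dropout and 1662 randomised, i.e. 831 per arm (11.1); imputation trigger above 10% missing (11.3.2).

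**Reproducing the planned size.** The plan says "at a two-tailed significance level of 0.05 with a power of 80% requires 1412 patients to be analysed, 706 per arm". With p̄ = 0.4625 and d = 0.075:

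n per arm = [1.96·√(2·0.4625·0.5375) + 0.8416·√(0.5·0.5 + 0.425·0.575)]² / 0.075² ≈ 693, or 1386 in total (1438 with continuity correction).

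A simulated Mantel-Haenszel test over 50 centres, using the centre variability described in 11.1, gives about 81.5% power at 1412. Also 1412 / 0.85 = 1661.2, rounded up to 1662. So 7.5 points is the right starting difference. The synopsis says "Assuming a 90-day mortality of 50% in the control group without albumin and 42% in the albumin group, 1412 patients need to be evaluated", but 42% gives 1218 (1266 with continuity correction) and does not reproduce 1412.

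**Dilution when arm is left out.** Assume the same missing share m in both arms, observed patients representative of their arm, and predictors that carry none of the treatment effect. Imputed patients then have one common mortality q:

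- mortality in an arm = (1 − m)·p_arm + m·q
- difference = (1 − m)·(p_control − p_albumin)
- m = 10%: 0.90 × 7.5 = 6.75 points (loss 0.75)
- m = 15%: 0.85 × 7.5 = 6.375 points (loss 1.125)

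Treating imputed values as if observed at 831 per arm, rough power is 0.866 at 7.5 points, 0.789 at 6.75 and 0.741 at 6.375. These figures ignore between-imputation variance and only indicate scale. If SOFA and length of stay carry part of the effect, the loss is smaller.

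**Simulation (all distributions assumed).** 1662 patients; SOFA mean 11, SD 3; 80% or 90% of 90-day deaths in hospital; stay of in-hospital deaths 1 day plus an exponential with mean 14 days; other stays 5 days plus a gamma with shape 2 and scale 14 days, all capped at 90; ICU stay equal to hospital stay for in-hospital deaths and 40–100% of it otherwise. **All missing patients were discharged alive.** Logistic imputation on SOFA, log hospital stay and log ICU stay; 100 replicates, 10 imputations each. The last model adds arm and is fitted only in patients discharged alive. Compare within rows, because the complete-data value varies by chance.

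| Missing | Deaths in hospital | Complete data | Listed predictors, no arm | Plus arm | Plus arm, fitted in live discharges |
|---|---|---|---|---|---|
| 10% | 80% | 7.56 | 7.04 | 7.45 | 7.50 |
| 10% | 90% | 7.21 | 6.79 | 7.09 | 7.18 |
| 15% | 80% | 7.40 | 6.64 | 7.33 | 7.47 |
| 15% | 90% | 7.72 | 7.10 | 7.61 | 7.74 |

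The loss without arm is 0.52, 0.42, 0.76 and 0.62 points.

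Mortality imputed among the missing, in the same row order:

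- listed predictors, with or without arm: 27.2%, 20.3%, 27.9%, 21.2%
- fitted in live discharges: 14.9%, 8.2%, 15.0%, 8.2%
- true: 14.5%, 7.8%, 14.6%, 8.1%

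At 15% missing, 0.15 × 1662 ≈ 249 patients are imputed: about 53 to 69 deaths (249 × 0.212 to 249 × 0.279) against about 20 to 36 true ones (249 × 0.081 to 249 × 0.146). Adding arm does not change the excess; conditioning on survival removes nearly all of it. The two omissions therefore need separate repairs.

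**The case against.** The strongest reply is that the protocol under-specifies the model rather than excluding anything. The mortality-rate item could mean rates by arm, or the 28-day, 60-day, ICU and hospital mortality that the same section lists next as secondary endpoints. That would bring in some of what appears to be missing. Section 11.3.2 also treats length of stay as ending at first discharge, with death and drop-out as censoring, so the stay data can distinguish the two endings. This stands as far as it goes: neither arm nor vital status is clearly ruled out. But the list does not name them, does not say how a censored stay enters the model, and the SAP does not fill the gap.

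A reader might infer that the imputation would place many deaths in patients already discharged alive. The documents do not support that. The simulated excess rests on the assumption that every missing patient left hospital alive. Section 11.1 also names failure of representative consent, which section 5.2.2 ties to 72-hour windows, when patients may still be in the ICU. The more missingness arises that way, the smaller the excess should be.

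A reader might also posit 20% missing in one arm and 10% in the other with a 19-point excess, giving (0.20 − 0.10) × 19 = 1.9 points of shift. Open-label treatment makes imbalance conceivable, but nothing in the documents supports those shares.

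Nor is it certain that the 10% trigger would be met. The 15% is a planning allowance, the rates printed beside it from two previous trials are 10.5% and 8.2%, and section 7.6 asks withdrawing patients for end-of-study data. Finally, this is a conditional sensitivity analysis, and dilution works against claiming a benefit.

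**Conclusion.** The point stands as a defect in a conditional sensitivity analysis, and it should be corrected. The primary analysis is not biased by it. The predictor list does not name arm, centre, the lactate stratum, SAPS II, baseline albumin or last known vital status.

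Leaving arm out costs at most the missing share of the effect: 0.75 of 7.5 points at 10% missing and 1.125 at 15%, given equal missingness in the arms and observed patients representative of their arm. Under the simulated assumptions the loss is about 0.4 to 0.8 points.

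Failing to condition on survival to last contact can impute too many deaths. The direction follows from the endpoint. The size cannot be fixed from the documents, because the split between loss after live discharge and early consent failure is not given.

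Separately, the protocol plans the imputation and the SAP rules it out without listing a deviation. Restoring the protocol's list unchanged would settle that conflict but leave the model deficient.

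**What to change.** Reinstate the imputation in the SAP (5.1 and 6.6) and bring the protocol and SAP into agreement; record any remaining difference in SAP 6.11. Replace the predictor list as follows:

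- impute within treatment arm, or with arm in the model;
- include the covariates of the primary model finally adopted, since the protocol and SAP versions differ, plus centre and the lactate stratum;
- condition on survival to the last date known alive, using vital status at discharge, day 28 and day 60, for example by drawing a death time from the arm-specific survival curve conditional on that date;
- if SOFA and length of stay are kept, state which SOFA values are used and how stays ending in death or drop-out are coded, and define or delete the mortality-rate item.

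A delta or tipping-point version by arm, and running the analysis whatever the percentage missing, are optional additions.

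The cost is wording in two documents and a little more programming. The vital-status data are already collected.
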